5.3.2. EXCLUSION CRITERIA

Subjects *will not be eligible for the study* if any of the following criteria are present:

- 1. Documented left atrial thrombus or another abnormality which precludes catheter introduction.
- 2. Documented ejection fraction (EF) < 40%.
- 3. Contraindication to anticoagulation therapy (heparin, warfarin, or novel oral anticoagulant [NOAC]).
- 4. Unstable angina or ongoing myocardial ischemia.
- 5. Myocardial infarction, unstable angina, cardiac surgery or coronary intervention within 3 months of enrollment.
- 6. Congenital heart disease where the underlying abnormality increases the risk of the ablation.
- Pulmonary hypertension (mean pulmonary artery pressure [mPAP] > 50 mmHg)
- 8. Enrollment in any other ongoing study protocol that would interfere with this study.

- 9. Documented severely impaired kidney function defined as Cockcroft-Gault Glomerular Filtration Rate (GFR) < 29ml/min.
- 10. Active gastrointestinal (GI) bleeding
- 11. Active infection or sepsis.
- 12. Short life expectancy (< 1 year) due to illness such as cancer, pulmonary, hepatic or renal disease.
- 13. Significant anemia (defined as hemoglobin < 8.0 gr/dL).
- Severe uncontrolled systemic hypertension with systolic blood pressure (SBP)
 > 200 mm Hg within last 30 days.
- 15. Severe bleeding, clotting or thrombotic disorder.
- 16. Uncontrolled diabetes.
- 17. Women who are pregnant or are not willing to use contraception for the duration of the study.
- 18. Severe chronic obstructive pulmonary disease (COPD; identified by a forced expiratory volume [FEV1] <1).
- 19. Prior stroke or TIA within the last 6 months.
- 20. Any other condition that, in the opinion of the investigator, poses a significant hazard to the subject if an ablation procedure was performed.

Additional exclusion criteria for AF patients only:

- 21. Left atrial diameter of > 55 mm (parasternal view).
- 22. Prior atrial septal defect (ASD) or patent foramen ovale (PFO) closure with a device using a transcatheter percutaneous approach.
- 23. Hypertrophic cardiomyopathy defined as left ventricular (LV) septal wall thickness >1.5cm.
- 24. Prior ablation or surgery for atrial fibrillation.
- 25. NYHA Class III or IV

5.4. STUDY PROCEDURES

Prior to recruitment of any subjects into the study, written approval of the protocol and informed consent must be obtained from the EC.

5.4.1. INFORMED CONSENT

The investigator will explain the study purpose, procedures, and subject's responsibilities to the potential participant and/or legal representative. Informed consent must be obtained from each subject prior to conducting any study related procedures including screening procedures that are not part of the standard of care at the institution. The subject's willingness and ability to meet the follow-up requirements will be determined, and written informed consent will be obtained. The subject will sign and date the informed consent form. The investigator will also sign and date the consent form. The original informed consent form will be retained with the subject records; a copy will be provided to the subject or legal representative.

Following is a detailed list of study visits from screening to final follow-up and the required procedures/tests. Methodologies for specific tests/procedures are described in Section 6.

5.4.2. SUBJECT IDENTIFICATION

To maintain confidentiality, the subject's name should not be recorded on any study document other than the informed consent form. A subject is considered enrolled after informed consent has been obtained. Each enrolled subject will be assigned a unique identifier in the following format: CP00001-XX-YYY. CP00001 is the study number, XX is the 2-digit assigned site number, and YYY is the 3-digit sequential subject ID number starting with 001. For example, the first subject at site 01 will be assigned CP00001-01-001. Subject ID numbers will not be re-used (e.g., if the subject is determined to be a screen failure).

5.4.3. VISIT 1: SCREENING (DAY -30 TO DAY 0)

Screening should be completed within 30 days of the index ablation procedure. Test results from routinely performed standard assessments may be used to determine eligibility. Prior to screening, the subject will provide informed consent and then be *initially* screened by review of relevant medical history including duration and frequency of arrhythmia(s), their subsequent treatments (e.g., medications, previous ablation) and associated symptoms.

If initial screening criteria are met, screening will proceed. Eligibility will be assessed sequentially, starting with the least invasive and least expensive tests as follows. *Results from each test / screening activity should be reviewed prior to proceeding to the next step.*

- Demographics
- Concomitant use of AADs and other important cardiovascular drugs medications
- Physical exam, including actual height
- Vital signs
- 12 lead EKG
- Labs:
 - Urine pregnancy test (for women of childbearing potential only)
 - Hematology
- Transthoracic echocardiography (TTE)
- Optional CT or MR imaging

5.4.3.1. SCREEN FAILURES

Subjects not meeting all study entry criteria will be designated as screen failures. End of study procedures will not be performed for these subjects, but their reason for ineligibility will be recorded on the Screening Log. Screen failures are not counted towards to total study enrollment.

5.4.4. VISIT 2: DAY 0 – INDEX ABLATION PROCEDURE

After documenting concomitant use of AADs and other important cardiovascular medications and confirming the absence of atrial thrombus or another abnormality precluding catheter introduction, catheters are introduced percutaneously and advanced to the chamber of interest. For left atrial procedures, if the esophagus is not mechanically deviated away from the left atrium, a temperature probe may be placed in the esophagus to monitor heating during the procedure.

The heart chamber is mapped using the Affera Sphere-9 Ablation Catheter and the Affera Mapping System to generate a representation of the heart and to locate the areas of the heart that are creating or propagating problematic electrical signals that interfere with the proper rhythm. In addition, pacing is used to identify the location of the phrenic nerve.

Ablation using the Affera Sphere-9 Ablation Catheter and the Affera RF Generator is performed, and data regarding ablation delivery is recorded by the Affera Mapping System. Procedural success is monitored by mapping and/or pacing to verify termination and non-inducibility of the arrhythmia (all subjects) and/or successful isolation of target pulmonary veins. Any serious procedural adverse events (AEs) will be documented.

Prior to discharge, the following will be documented:

- Vital signs
- 12-lead EKG
- Serious adverse events (AEs)

At the discretion of the investigator, the following assessments can be performed prior to discharge:

- Transthoracic echocardiography (TTE)
- Endoscopic evaluation of the esophagus
- CT or MR imaging

5.4.5. VISIT 3: DAY 10 ± 3 DAYS (TELEPHONE CALL)

The following assessments will be performed, optionally via a telephone call:

- Concomitant use of AADs and other important cardiovascular medications
- Serious cardiovascular AEs

5.4.6. VISIT 4: DAY 90 ± 14 DAYS

The following assessments will be performed:

- A minimum of 48 hours of ambulatory cardiac monitoring
- Episodes of treated arrhythmia greater than 30 second in duration
- Concomitant use of AADs and other important cardiovascular medications
- 12 lead EKG
- Serious cardiovascular AEs

At the discretion of the investigator, CT or MR imaging can be performed at this visit.

5.4.7. VISIT 5: DAY 180 ± 30 DAYS

The following assessments will be performed:

- A minimum of 48 hours of ambulatory cardiac monitoring
- Episodes of treated arrhythmia greater than 30 second in duration
- Concomitant use of AADs and other important cardiovascular medications
- 12 lead EKG
- Serious cardiovascular AEs

At the discretion of the investigator, CT or MR imaging can be performed at this visit.

5.4.8. VISIT 6: DAY 365 ± 30 DAYS

The following assessments will be performed:

- A minimum of 48 hours of ambulatory cardiac monitoring
- Episodes of treated arrhythmia greater than 30 second in duration
- Concomitant use of AADs and other important cardiovascular medications
- 12 lead EKG
- Serious cardiovascular AEs

At the discretion of the investigator, CT or MR imaging can be performed at this visit.

All subjects will exit the study after the Day 365 visit.

5.5. STUDY COMPLETION

5.5.1. COMPLETED SUBJECTS

Each subject in the study will be considered completed when all assessments through the Day 365 visit have been performed in accordance with the study protocol.

5.5.2. **DISCONTINUED SUBJECTS**

Any subject may voluntarily discontinue the study at any time without prejudice. The investigator may discontinue a subject from the study at any time if (s)he considers that remaining in the study compromises the subject's health or the subject is not sufficiently cooperative. In either event, reason(s) for discontinuation should be recorded.

Possible reasons for study discontinuation include the following:

- Adverse events (AEs) necessitating discontinuation from the study.
- Repeat ablation with a non-study device.
- Subject decision (specify).
- Investigator decision (specify).
- Other reason (specify).

The reasons for any subject discontinuation will be recorded on the study completion form of the study worksheets. If possible, subjects who withdraw prior to study completion will undergo the following:

- 12 lead EKG
- AE assessment
- Assessment of symptomatic episodes of the treated arrhythmia
- Concomitant medications

Lost to follow-up will only be considered at the Day 365 visit. Other follow-up visits will be considered missed visits if the subject is unable to attend. Every attempt must be made to have subjects complete the study. The investigator/designee must do his/her best to contact the subject by phone at least twice. If no response is obtained from the subject, the investigator/designee is encouraged to contact one of the subject's relatives or his/her general practitioner. Documentation of these contacts must be recorded in the subject's source.

5.5.3. **PREMATURE STUDY TERMINATION**

The Sponsor reserves the right to discontinue the study for any safety, ethical or administrative reason at any time.

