After confirmation of the absence of atrial thrombus precluding catheter introduction, eligible subjects will undergo mapping and ablation. Subjects will be assessed for potential adverse events prior to discharge. Esophageal evaluation, and CT and/or MR imaging may optionally be performed after treatment or during follow-up.

Subjects will be followed for approximately 365 days after the ablation procedure to characterize safety and product performance. Note, the Day 10 visit can be conducted by telephone. Ambulatory monitoring for a minimum of 48 hours will be conducted within the follow-up windows at Day 90, Day 180, and Day 365. Use of antiarrhythmic drugs and other important cardiovascular drugs will be collected at every visit. Serious adverse events (AEs) will be collected starting on Day 0 through study exit.

A summary of the schedules of evaluations and visits can be found in Appendix 1.

5.3. Subject Population

Up to a total of 30 subjects meeting the following study entry criteria will be treated.

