7.2. ASSESSMENT OF ADVERSE EVENTS

The need to capture AEs is not dependent upon whether or not the clinical event is associated with the use of the study device or procedure. All AEs, regardless of severity, occurring at the index ablation through study exit visit must be recorded. Events occurring prior to the endovascular procedure must be listed in the medical history.

The following information should be obtained for each AE:

1. Event description. Every effort must be made to report the underlying condition or unifying diagnosis for the event. To avoid vague, ambiguous or colloquial expressions, the AE should be recorded in standard medical terminology rather than the subject's own words when possible. Signs and symptoms that are considered unrelated to an encountered syndrome or disease should be recorded as individual AEs on the CRF (e.g., if congestive heart failure and severe headache are observed at the same time, each event should be recorded as an individual AE).

In addition, AEs occurring secondary to other events (e.g., sequelae) should be identified by the primary cause (i.e., a "primary" AE, if clearly identifiable, generally represents the most accurate clinical term to record on AE CRF; events occurring secondary to the primary event should be described in the narrative description of the case [e.g., example: orthostatic hypotension \rightarrow fainting and fall to floor \rightarrow head trauma \rightarrow neck pain; the primary AE is orthostatic hypotension]).

2. Duration: The date of onset and date of resolution should be reported. Every effort should be made to capture the exact dates.

3. Outcome: The final status of the event should be reported as resolved, ongoing, or if it resulted in death. If the event is present at the final study visit, the ongoing box must be marked.

4. Severity: The worst severity of the event must be reported as mild, moderate, or severe using the following definitions:

- Mild: Aware of sign or symptom, but easily tolerated
- Moderate: Discomfort enough to cause interference with usual activity
- Severe: Incapacitating with inability to work or do usual activity

5. Action taken: Treatment of the event may be reported as none, medical and/or surgical.

6. Seriousness: Determined by using the criteria in Section 7.1.

7. Relationship to device (study device or ancillary device), and procedure. The relationship to device and study procedure will be assessed using the following criteria.

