- Not related: no temporal association, or the cause of the event has been identified; or the device or procedure cannot be implicated
- Unlikely: the relationship with the use of the device seems not relevant and/or the event can be reasonably explained by another cause, but additional information may be obtained
- **Possible:** temporal association, but other etiologies are likely to be the cause; however, involvement of the device or procedure cannot be excluded
- **Probable**: the relationship with the use of the investigational device seems relevant and/or the event cannot reasonably be explained by another cause, but additional information may be obtained
- **Causal:** temporal association; other etiologies are possible, but unlikely

If any AE is considered to be "possibly related" or "related" to the use of the study device, that event will classed as an ADE or a SADE.

7.3. Reporting/Recording of AEs

Throughout the course of the study, all efforts will be made by the investigator to remain alert to possible AEs. The first concern will be the safety of the subject, and for providing appropriate medical intervention. The period of observation for collection of AEs starts at index ablation procedure until study exit. Any AE should be recorded on the appropriate study worksheet.

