8.2. STUDY OUTCOMES

8.2.1. SAFETY

The primary safety outcome is the rate of the following SAEs occurring starting Day 0 and extending through the Day 10 follow-up visit:

- TIA
- CVA
- Major bleeding
- Cardiac tamponade
- Pulmonary vein stenosis
- Severe pericarditis requiring hospitalization
- Myocardial infarction
- Diaphragmatic paralysis
- Atrio-esophageal fistula (through the Day 90 assessment)
- Valvular damage
- Phrenic nerve palsy
- Intra-procedural device complications requiring open chest or heart surgery
- Vascular complications requiring surgical intervention
- Death

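### Section 5.5.2 permits exit from the study after an adverse event or a non-study repeat ablation, and safety collection ends at exit, so late safety data can be lost in harmed or retreated subjects

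*Combined protocol and SAP*

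**What the plan says.** Section 5.5.2 gives possible reasons for discontinuation from the study. Two matter here: "Adverse events (AEs) necessitating discontinuation from the study" and "Repeat ablation with a non-study device". The same section adds a discretionary route: "The investigator may discontinue a subject from the study at any time if (s)he considers that remaining in the study compromises the subject's health".

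Safety collection is tied to study exit. Section 5.2 states: "Serious adverse events (AEs) will be collected starting on Day 0 through study exit". Section 7.3 states: "The period of observation for collection of AEs starts at index ablation procedure until study exit".

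For early leavers, Section 5.5.2 says: "If possible, subjects who withdraw prior to study completion will undergo the following". The list that follows is a 12-lead EKG, an AE assessment, symptomatic episodes and medications. For an unresolved event, Section 7.2 says: "If the event is present at the final study visit, the ongoing box must be marked".

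The safety horizons run later than an early exit might. In Section 8.2.1 all primary safety components close at the Day 10 visit except one, whose entry begins "Atrio-esophageal fistula (through the Day 90 assessment". Section 5.2 plans about 365 days of follow-up for safety as well as performance.

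**The concern.** The investigational exposure is a single procedure on Day 0. The later visits (Sections 5.4.5 to 5.4.8) consist of contacts, EKGs, at least 48 hours of ambulatory monitoring, medication review and serious event review, with imaging optional. No continuing study treatment is left for an adverse event to interrupt, so discontinuing a subject from the study mainly stops the looking.

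The subjects who may leave by these routes are those who were harmed or needed more treatment. Missing late safety data would then be related to outcome, which makes it harder to interpret than ordinary attrition. The repeat-ablation route is foreseeable: the Introduction itself describes repeat procedures as often needed in AF and sometimes needed in flutter.

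At stake are the Day 90 fistula component, the one-year profile of serious events, and the final outcome of the event that led to exit.

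**Working it through.** The plan states no derived figure to reproduce. Section 8.1 says that no formal hypothesis underlies the sample size, and no dropout or exit rate is given. The check is therefore a comparison of the rules, followed by arithmetic for scale.

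**Rules side by side**

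1. May a subject leave after an AE or a non-study repeat ablation? Yes, as a possible reason (5.5.2). It is not mandatory.
2. When does safety collection stop? At study exit (5.2, 7.3). Section 5.4.8 has all subjects exit after the Day 365 visit, but 5.5.2 treats discontinued subjects as leaving before completion. Exit therefore cannot be read as Day 365 for them.
3. Is anything collected after discontinuation? No section requires later collection of serious events or vital status.
4. Must an event open at exit be followed to its end? No section requires it. Section 7.2 has it recorded as ongoing.
5. How do early leavers enter the safety results? Section 8.3 summarizes missing data but gives no rule for the safety denominator.

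**Which primary components are exposed**

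Section 8.2.1 lists 14 components. One, atrio-esophageal fistula, runs to Day 90, and 14 − 1 = 13 close at Day 10. Those 13 are affected only if a subject leaves before the Day 10 contact.

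**Scale**

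Inputs: N = at most 30 treated (5.3); horizons of 90 and 365 days (8.2.1, 5.2). Assumptions: exit on Day 30, and m = 1 to 3 early exits.

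- Fistula window unobserved: 90 − 30 = 60 of 90 days (67%).
- Serious event follow-up unobserved: 365 − 30 = 335 of 365 days (92%).
- Share of the cohort per subject: 1/30 = 3.3%, and more if fewer than 30 are treated. Three subjects: 3/30 = 10%.

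Suppose no late event is seen in the subjects who stay. The two-sided exact 95% upper bound for 0 events in n is 1 − 0.025^(1/n). With all 30 followed it is 1 − 0.025^(1/30) = 11.6%. With m subjects unobserved, the full-cohort result could lie anywhere from 0/30 to m/30:

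| m (assumed) | Observed | 95% upper bound | If all m had the event | Exact 95% CI |
|---|---|---|---|---|
| 1 | 0/29 | 11.9% | 1/30 = 3.3% | 0.1% to 17.2% |
| 2 | 0/28 | 12.3% | 2/30 = 6.7% | 0.8% to 22.1% |
| 3 | 0/27 | 12.8% | 3/30 = 10.0% | 2.1% to 26.5% |

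The fourth column is an extreme bound, not an expectation. Losing one to three subjects at random barely moves the upper bound (11.6% to 12.8%). What matters is that the loss may not be random.

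**The case against.** The case on the other side is substantial.

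- **The wording is permissive.** The items are possible reasons, and the AE item covers only events that necessitate leaving. Nothing forces a harmed or re-ablated subject out. This stands, and the point claims only that early exit is allowed and that nothing follows it.
- **There are safeguards.** Section 5.5.2 asks sites to try hard to keep subjects to completion, treats absences before Day 365 as missed visits, and provides for contact by telephone or through relatives or the general practitioner. These help with subjects who stop responding. They set no rule for a subject discontinued for a listed reason.
- **The event that triggers exit is already recorded.** It occurs before exit, so its worst severity is reportable under Section 7.2. A reader might infer that its outcome is never obtained. The documents do not support that: there is an exit AE assessment where possible, and Section 7.4 calls for detailed written reports, lets the sponsor request more information, and seeks an autopsy report or death summary after a death. What is missing is a duty to follow the event to resolution.
- **No rule counts early leavers as event-free.** A reader might infer that they enter the results as having no further events, which would bias rates downwards. No section says so, and Section 8.3 reports missing data. Incomplete observation is shown; that coding is not.
- **There is no contradiction with the 365-day plan.** A discontinuation clause beside a planned follow-up period is ordinary. The gap is what happens after discontinuation.
- **The complication rate of 2–3% in the Introduction does not size this.** It is an overall rate, not a rate of exit or of missed late events.

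**Conclusion.** The point holds in limited form. A site that follows the written rules can stop safety observation of a harmed or retreated subject before Day 90 or Day 365 without a deviation. Fistula through Day 90, serious events through Day 365 and the final outcome of events open at exit may then be incompletely observed.

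A reader might infer that the primary safety outcome as a whole is compromised. It is not: 13 of its 14 components close at Day 10 and are largely unaffected.

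The bias cannot be quantified, because no exit rate is given. Each early exit is at least 3.3% of the cohort; the Day 30 exit and the one to three exits used above are assumptions. In a descriptive study of at most 30 subjects this is a change that should be made because it is cheap. It does not invalidate the design. Whether a given event ought to end a subject's participation is a clinical matter and is not judged here.

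**What to change.** 1. **Sections 5.5.2 and 7.3:** state that, unless the subject withdraws consent, collection of serious events and vital status continues after discontinuation, by telephone or record review, at whichever of the Day 10, 90, 180 and 365 time points remain. Flag events that occur after a non-study repeat ablation.
2. **Section 8:** report the number of subjects with complete safety follow-up at Day 90 and at Day 365 as the denominator, alongside all treated subjects.
3. **Section 7.2:** require serious events judged related to the device or procedure and still open at exit to be followed until resolved or stable.

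Deleting the two listed reasons is optional once the first sentence is in place. On its own it would change little, because investigator decision, other reasons and the health-based discretion would remain.

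The cost is a wording amendment, a few added telephone or record-review contacts (only Day 10 is already an optional telephone visit), and limited tracking of open events past exit.
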